## **2.2 Study design**

This Phase IIb extension study is a 24 weeks off drug follow-up observation trial to determine the durability of effect and the safety of bimagrumab in older patients with sarcopenia.

[figure not shown]
After completing 24 weeks of treatment in the core study (CBYM338E2202), newly consenting patients in the extension study CBYM338E2202E1 will continue with the same uniquely identified patient number and be followed for an additional 24 weeks off drug. They will complete the EOS at week 49.

**Figure 2-1 Study design for patients enrolled after the protocol amendment #1**

Patients enrolled prior to protocol amendment #1 will follow the original study design and will continue to be treated as per the regimen assigned at the entry of the extension study.

**Figure 2-2 Study design for patients enrolled prior to protocol amendment #1**

### 3 Statistical and analytical plans

The planned analysis is described in [Section 9](#) of the protocol ([Appendix 16.1.1](#)).

The primary objective of this study is to assess the durability of effect of bimagrumab (BYM338) in older adults with sarcopenia as measured by week 49 SPPB.

Unless otherwise stated, summary tables/figures/listings will be on all subjects included in the population under consideration. Data will be summarized with respect to demographic and baseline disease characteristics, efficacy, and safety assessments.

#### 3.1 Statistical methods: Analysis sets

The following analysis sets are defined:

**Full analysis set (FAS):** The FAS comprises of all subjects enrolled in the study.

**Safety set (SAF):** The safety set comprises of all subjects who received at least one dose of study drug from the core or extension study and enrolled in the extension study. Subjects will be analyzed according to the treatment actually taken.

**Per-protocol set (PP):** The Per-protocol set comprises all subjects in the FAS who do not have major deviations that could confound the interpretation of analyses conducted on the FAS. The following are common examples of such protocol deviations:

- Subject entered the study even though they did not satisfy the entry criteria
- Subject developed study/treatment withdrawal criteria during the study but was not withdrawn
- Subject received the wrong treatment or incorrect dose
- Subject took a prohibited concomitant medication

The PP set will be identified and finalized based on blinded review of the data, prior to the final database lock.

[REDACTED]

To facilitate different analysis on patients enrolled before and after the protocol amendment #1, two populations are defined as below:

- Population I is defined to include patients enrolled prior to protocol amendment 1, who will be continuing the treatment as originally assigned and follow the original schedule until end of the study.
- Population II is defined to include patients enrolled after protocol amendment 1, who will be followed up per schedule defined in this protocol amendment.

### **3.2 Patient disposition, background and demographic characteristics**

The analysis in this section will be based on FAS. For Population I, all summaries will be presented by treatment group in the extension study and overall. For Population II, all summaries will be presented by treatment assigned in the Core study and overall.

Relevant raw and derived data as described in this section will be presented in by-patient data listings. All by-patient data listings will be sorted by Population, treatment group, [REDACTED] center and patient if not indicated otherwise.

Where relevant, “overall” refers to the addition of a “Total” treatment column within the planned presentation of the data.

#### **3.2.1 Patient disposition**

All patients will be summarized using number (n) and percentage (%), overall [REDACTED] center, by each treatment group and overall, for [REDACTED]

Populations I and II separately. Furthermore, for each study epoch (screening, treatment and follow-up as applicable to the populations) the number of patients per treatment group and the overall number of patients who entered the epoch, completed, and discontinued within the epoch will be summarized in a similar manner, including the reasons for discontinuation.

At the final analysis, the number (n) and percentage (%) of patients with protocol deviations will be summarized by category and deviation, for each treatment group and overall, [REDACTED]. Patients with protocol deviations will be listed.

The number (n) and percentage (%) of patients included in each analysis set will be summarized by treatment group and overall, [REDACTED] for Populations I and II separately. At the final analysis, the reasons for exclusions from analysis sets will be tabulated overall for all patients [REDACTED] for each treatment group and overall. Patient exclusion from analysis sets will be listed for all patients with reason(s) for exclusion, including both major protocol deviations and/or other exclusion criteria.

### **3.2.2 Patient demographics and other baseline characteristics**

Descriptive statistics for demographics and baseline characteristics at Week 25 will be presented to describe the FAS. All summaries will be presented by treatment group and overall [REDACTED] for Populations I and II separately.

Descriptive statistics (n, mean, median, standard deviation, minimum and maximum (not for IA), Q1 and Q3) will be presented for continuous variables for each treatment group and overall in the FAS. The number and percentage of subjects in each category will be presented for categorical variables for each treatment group and overall. Unless otherwise specified, percentages will be based on the number of patients in the FAS with data available.

#### **3.2.2.1 Demographics**

Demographic variables taken at screening, including age, sex, child bearing potential of female subjects, height (cm), weight (kg), body mass index (BMI) (kg/m^2), race and ethnicity will be summarized.

#### **3.2.2.2 Other patient characteristics**

Patient characteristics at Week 25 will be summarized. Patient characteristics will include: nutritional status, protein intake, total and appendicular lean body mass (LBM and ASMI), 6 minute walk test (6MWT), Gait Speed, Short Physical Performance Battery (SPPB) total score, [REDACTED].

##### **3.2.2.2.1 Nutritional status/protein intake**

For both populations, nutritional status at Week 25 will be summarized by both descriptive measures for quantitative variables (calculated protein intake) and qualitatively for patient's daily protein intake categories (< 0.8 grams protein/kg and ≥ 0.8 grams protein/kg), nutritional

status (sufficiently nourished/malnourished), and action taken if malnourished if available (dietary counseling with or without intervention/no dietary counseling).

### 3.2.2.2.2 Efficacy assessments

#### **Total LBM, ASMI**

Week 25 data (all relevant pre-treatment assessments, including baseline value, relative to Week 25) of total LBM, ASMI will be summarized using descriptive statistics for both population I and population II, separately.

#### **Six Minute Walk Test (6MWT)**

The 6 minute walk test (6MWT) is a simple, economical and reproducible test that measures how many meters a person can walk in 6 minutes. All subjects will be included in the descriptive statistics with the actual distance walked. In circumstances where the test is interrupted for reasons other than patient fatigue the test may be repeated once, preferably on the same day (with a minimum 20 minute rest period). Total distance walked will be summarized by descriptive statistics. Walking aids used for the test will be summarized by category as defined in the CRF page.

Summaries at Week 25 will be provided for both population I and population II, separately.

#### **SPPB**

The short physical performance battery (SPPB) evaluates lower extremities in three functional components: Standing balance, gait speed and chair stand. A score will be calculated for each of the three components. In addition a total SPPB score will also be calculated. Total standing balance score is calculated as the sum of the scores of side-by-side stand, semi-tandem stand and tandem stand.

- Side-by-side stand: held for 10 sec = 1 point, not held for 10 sec or not attempted = 0 points.
- Semi-tandem stand: held for 10 sec = 1 point, not held for 10 sec or not attempted = 0 points.
- Tandem stand: held for 10 sec = 2 points, held for 3 to 9.99 sec = 2 points, held for less than 3 sec or not attempted = 0 points.

Gait speed will be assessed as part of the SPPB, over a 4 meter distance of a 6 or 4 meter course. Gait speed assesses a person's usual walking speed. The patient will perform two recorded trials of walking across the defined course. The fastest time in seconds (to the nearest 0.01 sec will be recorded. If only one walk was performed, this time will be used. Any walking aid(s) used during the SPPB gait speed test performance will be captured in the eCRF. The scoring system is as follows:

- Time < 4.82 sec = 4 points.
- Time ≥ 4.82 to ≤ 6.20 sec = 3 points.
- Time ≥ 6.21 to ≤ 8.70 sec = 2 points.
- Time > 8.70 sec = 1 point.

- Patient is unable to do the walk = 0 points.

At first the chair stand test will be done one time (singular chair stand test). If the patient used arms to stand or the test could not be completed then the test procedure will be stopped and the score for the test is 0 points. If the patient stood up without using arms the aim of the second part of the test is to stand up five times (repeated chair stand test). The scoring system is as follows:

- Time to complete 5 stands  $\leq 11.19$  sec = 4 points.
- Time to complete 5 stands  $\geq 11.20$  to  $\leq 13.69$  sec = 3 points.
- Time to complete 5 stands  $\geq 13.70$  to  $\leq 16.69$  sec = 2 points.
- Time to complete 5 stands  $\geq 16.70$  to  $\leq 60$  sec = 1 point.
- Patient is unable to complete 5 chair stands or has completed stands in  $> 60$  sec = 0 points.

The total SPPB score will be calculated as the sum of the total standing balance score, gait speed test score and chair stand test score.

Handling of missing data: If a test is not done (i.e. test not done is ticked in the eCRF) there will be no imputation of data. Since the standing balance tests become progressively more difficult with each test, if the result for the tandem stand or semi-tandem stand is missing the result will be imputed by 0 points, provided that the previous test(s) had been performed. In all other cases there will be no imputation.

Week 25 data (all relevant pre-treatment assessments, including baseline value, relative to Week 25) of the total SPPB score with the corresponding scores of the three individual component tests: Standing balance, gait speed, and chair stand will be tabulated in a frequency table. Categories for each of the individual component tests will be:

- 0 points.
- 1 point.
- 2 points.
- 3 points.
- 4 points.

Categories for the total SPPB score will be:

- 0 to 6 points.
- 7 to 9 points.
- 10 to 12 points.

In addition to the scores, the actual time of the timed function tests will be summarized for the individual components using descriptive statistics (see Section 5.22.1 [Precision and summary statistics]). For balance tests, if the patient attempted the test and is indicated as “Held for 10 seconds” then a value of 10 seconds will be used.

If a patient did not attempt a test or failed, the patient will have a missing time for that test.

[figure not shown]

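### The SPPB balance rule scores a blank harder stand as 0 when the easier stand was merely performed, not failed, so a patient's primary score can be up to 2 points too low

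*SAP*

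**What the plan says.** SAP section 3.2.2.2.2 (SPPB) builds the balance score as the sum of three stands, and the SPPB total as the sum of balance, gait speed and chair stand. Semi-tandem scoring reads "Semi-tandem stand: held for 10 sec = 1 point, not held for 10 sec or not attempted = 0 points"; side-by-side is scored the same way. A full 10-second tandem hold scores 2, and the rest of that line reads "held for 3 to 9.99 sec = 2 points, held for less than 3 sec or not attempted = 0 points".

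The missing-data paragraph in the same section has three parts:

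- A general rule: "If a test is not done (i.e. test not done is ticked in the eCRF) there will be no imputation of data".
- A balance exception. The reason comes first, "Since the standing balance tests become progressively more difficult with each test", then the trigger, "if the result for the tandem stand or semi-tandem stand is missing", then the action, "the result will be imputed by 0 points, provided that the previous test(s) had been performed".
- A closing rule: "In all other cases there will be no imputation".

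SAP section 3.4.3 applies this exception to the primary endpoint, SPPB at Week 49 (citing it as section 1.3.2.2.2; the rule is in 3.2.2.2.2). SAP section 5.6 imputes nothing else unless otherwise indicated. Protocol section 9.4.3 plans observed data only, with no balance exception.

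**The concern.** The reason and the condition do not match. If the stands get harder, failing an easier one justifies a zero on the next. Having performed the easier one does not, because performing includes holding it for the full 10 seconds. For a patient who held both easier stands, the evidence points towards ability, yet the rule assigns the lowest possible tandem score.

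The wording is also incomplete for the patient it best suits. Someone who fails side-by-side and stops has no semi-tandem or tandem result. If those fields are blank, semi-tandem is imputed as 0, but the stand before tandem was not performed, so on a strict reading tandem is not imputed and the total cannot be summed.

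The primary endpoint is affected at Week 49. Week 25 SPPB, the covariate in the exploratory Population II ANCOVA of SPPB (SAP sections 3.5.3.1 and 5.8.2), is derived in the same way.

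**Working it through.** **Inputs.** Stand scores: side-by-side 0 or 1, semi-tandem 0 or 1, tandem 0 or 2 as printed (SAP 3.2.2.2.2). Scale 0–12 and clinically relevant change 1.0 (protocol 6.3.2). Planned 40 to 50 patients per bimagrumab dose arm, with 95% half-widths (protocol Table 9-2, SAP Table 3-1).

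**The plan's own figures.** Half-width = 1.96 × SD / √n, for SD 1.5, 2.0, 2.5, 3.0:

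- n = 50: 0.416, 0.554, 0.693, 0.832 (stated 0.42, 0.55, 0.69, 0.83)
- n = 40: 0.465, 0.620, 0.775, 0.930 (stated 0.46, 0.62, 0.77, 0.93)

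These agree. The scale also agrees: balance maximum 1 + 1 + 2 = 4, total maximum 4 + 4 + 4 = 12.

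**Balance score by pattern.** Blank here means no result, no not-done tick and no entry of not attempted. Strict means every earlier stand must have a result; broad means a side-by-side result is enough. The range is arithmetic only: each blank stand takes its lowest and highest score.

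| Side-by-side | Semi-tandem | Tandem | SAP, strict | SAP, broad | Range | Proposed rule |
|---|---|---|---|---|---|---|
| held | held | blank | 2 | 2 | 2 to 4 | missing |
| held | blank | held | 3 | 3 | 3 to 4 | missing |
| held | failed | blank | 1 | 1 | 1 to 3 | 1 |
| failed | blank | blank | missing | 0 | 0 to 3 | 0 |
| held | blank | blank | missing | 1 | 1 to 4 | missing |

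In rows three and four an easier stand was failed, so the SAP's difficulty argument supports the lowest value, and the proposed rule gives it. Row one is the main defect: the SAP gives 2 and the true score may be 4. With one blank stand the largest understatement is 2 points (tandem) or 1 point (semi-tandem). Only the broad reading of row five reaches 4 − 1 = 3.

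**Effect on an arm mean.** Shift from one patient with a 2-point error = 2 / n:

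- n = 50: 2 / 50 = 0.04
- n = 40: 2 / 40 = 0.05

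Both are small against half-widths of 0.42 to 0.93.

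**Population I, under an assumption.** Protocol 3.1 expects about 45 patients, and protocol 5.2 splits each of four core groups 1:1, giving eight groups. If the core groups were of equal size (sizes are not given), 45 / 8 = 5.6, about 6 per group, and one such error would move a group mean by 2 / 6 = 0.33. Intervals from groups that small are also much wider than those tabulated.

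**The case against.** The strongest reply is that the SAP separates three data states. A stand not attempted is scored 0 directly, without imputation. A test ticked as not done is left unimputed. Only a blank result falls under the exception. The false zero then needs a tandem field left blank with neither entry, after two successful holds. Validation checks, queries and full source verification of primary data (protocol 8.1 to 8.3) should make that uncommon. Sites and patients remain blinded (protocol 3.2 and 5.4), nothing suggests that the error differs between arms, and no hypothesis is tested.

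Most of this stands, and it limits the point. It does not repair the rule: when a blank does survive the checks, the SAP prescribes a zero that its own rationale does not support. Nor does cancellation between arms settle the matter, because the primary Population II output is a summary for each arm, where a lowered level does not cancel.

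A reader might go further in four ways that the documents do not support:

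- **That the not-done and not-attempted rules contradict each other.** This assumes the eCRF merges the two states. The eCRF and the Outcomes Manual are not among the documents. What can be said is that the SAP defines neither the terms nor their precedence.
- **That the plan drops the least able patients.** A later stand recorded as not attempted after a failure scores 0, so the total survives. It is lost if the fields are blank and the condition is read strictly, or if the not-done tick is used.
- **That arm means shift by 0.06 to 0.20.** This assumes that 3 to 10% of an arm is affected, a rate with no source, and gives every case the maximum 2-point error.
- **That gait speed and chair stand need the same change.** Inability already scores 0 for both, and a ticked not done is already left unimputed.

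**Conclusion.** The concern holds in a narrow form. The condition for imputing a zero is looser than the reason given for it, and the rule feeds the primary endpoint. For a patient who held both easier stands and has a blank tandem result, the score may be too low by up to 2 points, twice the clinically relevant change. The error is zero if that patient would in fact have failed the tandem stand. On a strict reading, blank fields after a failed first stand lose the total, but this depends on how sites record the stop.

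At the planned arm sizes the effect per case is slight, 0.04 to 0.05 on the mean. Overall importance depends on how often such blanks remain after data cleaning, which the documents do not say and which is probably seldom. This is a scoring rule worth correcting because the correction is cheap, not a threat to the study's conclusions.

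**What to change.** Replace the balance exception in SAP section 3.2.2.2.2:

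- Impute 0 for a missing semi-tandem or tandem stand only if an easier stand was not held for 10 seconds, or if the stand is recorded as not attempted because the patient was unable or unsafe. Every harder stand without a result then also scores 0.
- If the easier stand was held and the next is blank for another or an unknown reason, query it. If the query does not resolve it, leave the balance component, and so the total, missing.
- State how a ticked not done, a recorded not attempted and a blank each map to 0 or missing, and which rule takes precedence.

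Correct the cross-reference in SAP section 3.4.3 and note there that the exception departs from protocol section 9.4.3. Gait speed and chair stand need no change.

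The cost is a few SAP sentences, a change to the derivation code and some site queries, all before final database lock. The downside is possibly a few more missing totals, where the present rule would supply an unsupported zero.

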### 3.4.3 Handling of missing values/censoring/discontinuations

Summary statistics will be provided for observed data (no imputation in general, except special cases of the balance test described in section 1.3.2.2.2).

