### 3.4.4 Supportive analysis

The same analysis will be performed on the PP analysis set [REDACTED] in two ways:

- [REDACTED]
- [REDACTED]
- [REDACTED]
- [REDACTED]

Proportions of patients being sarcopenic at Week 25 and Week 49 will be summarized by treatment, for population I and II separately. The criteria of being sarcopenic are from core study protocol inclusion criteria:

- Gait speed < 0.8 m/sec
- ASMI  $\leq 7.26 \text{ kg/m}^2$  for men and  $\leq 5.5 \text{ kg/m}^2$  for women, or for Asian countries  $\leq 7.0 \text{ kg/m}^2$  for men and  $\leq 5.4 \text{ kg/m}^2$  for women

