### 3.5.1 Variables

Secondary efficacy variables include:

- 6MWT at Week 49
- Gait speed at Week 49
- Total LBM and ASMI as measured by DXA at Week 49

- [REDACTED]

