## 5.6 Handling of missing values/censoring/discontinuations

In general, unless otherwise indicated, no data imputation will be done for the missing values.

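### Patients unable to do the 4 m walk have no Week 49 gait speed, although the same inability scores 0 in the SPPB; their sarcopenia status is undefined

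*SAP*

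**What the plan says.** **Source of gait speed.** The SAP (SPPB) states: "Gait speed will be assessed as part of the SPPB, over a 4 meter distance of a 6 or 4 meter course". Protocol 6.3.3 also takes gait speed from the SPPB walk. No other gait test is described.

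**Time when the walk is failed or not attempted.** SAP, SPPB: "If a patient did not attempt a test or failed, the patient will have a missing time for that test".

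**Score for the same inability.** SAP, SPPB: "Patient is unable to do the walk = 0 points". The patient keeps an SPPB total and stays in the primary endpoint.

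**Imputation.** After the exception for the semi-tandem and tandem stands, the SPPB section says: "In all other cases there will be no imputation". SAP 5.6 says: "In general, unless otherwise indicated, no data imputation will be done for the missing values". For the primary endpoint, SAP 3.4.3 says: "no imputation in general, except special cases of the balance test described in section 1.3.2.2.2".

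**Where gait speed is used.** SAP 3.5.1 lists "Gait speed at Week 49" as a secondary variable. It enters the descriptive statistics (3.5.2), the Population I t-intervals (3.5.3.1, 5.8.1) and the Population II ANCOVA (3.5.3.1, 5.8.2).

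**Sarcopenia.** SAP 3.4.4 summarises the proportion sarcopenic at Weeks 25 and 49. It lists "Gait speed < 0.8 m/sec" together with a low-ASMI criterion. It gives no denominator and no rule for a missing gait speed.

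**The concern.** One event, being unable to walk 4 m, is handled in two ways. In the SPPB it is the worst result and is counted. In gait speed, taken from the same walk, it produces no value. The missingness is informative, because the patient lacks a speed precisely because function has been lost.

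The study asks whether function lasts after treatment stops, and losing the ability to walk is a plain failure of durability. A walkers-only mean cannot show it. The planned count of non-missing observations does not reveal it either, because that count mixes patients who were unable with those who did not attend. The SPPB component frequency table, which would show gait scores of 0, is specified in the visible text only for Week 25.

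A second gap follows. A patient who cannot walk is clearly on the slow side of the sarcopenia gait cut-off but has no value to compare with it. The programmer would have to choose a classification and a denominator.

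**Working it through.** **1. The plan's own figure.** The only precision calculation is the half-width of the 95% interval for mean SPPB (Protocol Table 9-2, SAP Table 3-1). With 1.96 × SD / √n, SD 2.0 and n = 40, it gives 1.96 × 2.0 / 6.325 = 0.62, as stated. The other seven cells also reproduce. The table does not bear on gait speed. The documents give no expected number unable to walk and no mean or SD for gait speed, so what follows is illustration under stated assumptions.

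**2. Does the rule reach Week 49?** There are two routes.
- The missing-time sentence sits in SAP 3.2.2.2.2, on Week 25 characteristics. That section holds the only visible SPPB and gait derivation rules, and 3.4.3 appears to point back to it, although only for the balance test and with a faulty section number.
- Without that sentence, a walk that was not completed still yields no time, and 5.6 bars imputation.

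Both routes leave the patient without a Week 49 gait speed.

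**3. Effect on one arm's mean.** Inputs: n patients assessed; k of them unable; walkers' mean m (assumed 0.7 to 0.9 m/s).
- Observed-data mean: m
- Mean with inability at 0 m/s: m(n − k)/n
- Gap: m × k/n = f × m, where f = k/n

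| n | m (m/s) | k = 1 | k = 2 | k = 4 |
|---|---|---|---|---|
| 40 | 0.7 | 0.018 | 0.035 | 0.070 |
| 40 | 0.8 | 0.020 | 0.040 | 0.080 |
| 40 | 0.9 | 0.022 | 0.045 | 0.090 |
| 28 | 0.8 | 0.029 | 0.057 | 0.114 |

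Here 40 is the lower planned size of a bimagrumab arm, and 28 = 40 × 0.7 applies the protocol's 30% drop-out assumption.

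**4. Effect on a difference between arms A and B.** The unadjusted difference moves by f_A·m_A − f_B·m_B. With m = 0.8 and n = 40 in both arms:
- 1 unable in A, 4 in B: 0.02 − 0.08 = −0.06 m/s
- 4 unable in A, 1 in B: +0.06 m/s
- equal numbers: 0

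The sign depends on which arm has more patients unable to walk.

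**5. Sarcopenia.** The cut-off of 0.8 m/s over 4 m is 4/0.8 = 5.0 s, so inability falls on the slow side. Assume 40 patients, 4 of them unable, and 18 of the 36 walkers sarcopenic.
- The 4 excluded: 18/36 = 50%
- The 4 counted as sarcopenic: 22/40 = 55%
- The 4 counted as not sarcopenic: 18/40 = 45%

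If both criteria are required, as the list suggests, ASMI decides which answer is right. If all four have low ASMI, exclusion understates the proportion (50% against 55%). If all four are above the ASMI cut-off, exclusion overstates it (50% against 45%).

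**6. Cost of scoring zeros.** With 39 walkers at mean 0.8 and SD s, plus one zero, the variance is [38s² + (39/40) × 0.64]/39.
- s = 0.15: (0.855 + 0.624)/39 = 0.0379, SD 0.195, about 30% larger
- s = 0.25: (2.375 + 0.624)/39 = 0.0769, SD 0.277, about 11% larger

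Both values of s are assumed. Population I has about 45 patients. Over seven groups (three doses, each continued or switched, plus placebo) and assuming equal sizes, that is about 6 each. One zero then moves a mean by 0.8/6 = 0.13 m/s.

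**The case against.** **The sentence is about times at Week 25, and for a time summary it is right.** This stands as a limit: its use at Week 49 is inferred. The consequence does not depend on it, because the no-imputation rule leads to the same place.

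**Zero is a choice, not the true value.** A summary among those who walked is a legitimate estimand in a study with no formal hypothesis testing, and inability already counts in the primary SPPB total. This also stands. The gap of f × m measures the distance between two definitions; it is not an error against a known truth. It supports keeping the observed-data summary and showing the other analysis beside it.

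**The event is probably rare.** Patients are community-dwelling, completed 24 weeks of core treatment and follow an exercise programme. Walking aids are recorded in the gait test, so needing an aid does not in itself remove the time. No figure in the documents supports a share as high as 10%. This stands and keeps the point minor.

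**Two stronger readings are tempting.** A reader might infer that dropping non-walkers makes bimagrumab's effect look more durable. The documents do not support that as a general claim. A single arm's mean is raised, but the planned Population I intervals and the Population II ANCOVA compare arms, and if more core-placebo patients lose the walk, excluding them works against bimagrumab. A reader might also infer that the proportion sarcopenic at Week 49 falls. SAP 3.4.4 sets no denominator and also lists ASMI. The data-available denominator is stated only for the baseline section (3.2.2), and SAP 5.2 allows a missing category where appropriate. The direction is therefore open.

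**Conclusion.** The point holds as a minor gap with a definite consequence. In the visible text, patients unable to do the 4 m walk have no Week 49 gait speed, while the SPPB counts the same inability as 0. Each arm's gait-speed mean is a walkers-only mean, higher than one with inability at 0 m/s by about 0.02 m/s per non-walker in 40, or about 0.03 m/s per non-walker in 28. These figures assume a walkers' mean of 0.8 m/s. The number unable cannot be derived from the documents. The effect on between-arm differences has no fixed sign.

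Sarcopenia status at Week 49 is undefined for these patients. In the illustration with 4 of 40 unable, the result runs from 45% to 55% depending on the rule chosen, and the direction of any distortion depends on the denominator and on ASMI. Inability to walk does not remove a patient from the primary endpoint. A test ticked as not done is a different case and is left without imputation.

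**What to change.** Amend the SAP before unblinding:

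1. Separate unable to walk from not done for other reasons. The SPPB scoring already makes this distinction (0 points against no imputation), so the gait component score should identify the patients, provided the eCRF records it that way.
2. Report the number unable by arm and visit for both populations.
3. Analyse gait speed with inability set to 0 m/s, at least as a sensitivity analysis beside the observed-data summary. Lead with medians and quartiles, which are already planned.
4. For the sarcopenia proportion, count inability as meeting the gait criterion, still apply ASMI, and state the denominator and how other missing values are shown.
5. State that these rules apply at every visit, and correct the section reference in 3.4.3.

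No new visits or assessments are needed. The cost is SAP wording, some programming and added variance. A few zeros skew the distribution and widen the t and ANCOVA intervals: one zero in 40 raises the SD by about 11% to 30% under the assumptions above. The effect is largest in the small Population I arms, and a median does not repair those intervals. The change does nothing for patients who miss the Week 49 visit.
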